Methodology / Design	
Non-randomised open label diagnostic study
 
We are planning to record 250 pre-defined abnormal ECGs (50 each of atrial fibrillation, atrial flutter, pre-excitation, ventricular tachycardia, , supraventricular tachycardia) and 150 control ECGs (100 sinus rhythm, 50 sinus tachycardia) using both the AliveCor Smartphone device and a 12-lead ECG. All 400 ECGs will then be read by 3 blinded reporters – a Consultant Electrophysiologist, a Consultant General Cardiologist and a General Practitioner. The output of the AliveCor automatic detection algorithm will also be recorded as a fourth reporter. The screening characteristics of all 4 reporters using the AliveCor device vs the definitive 12 lead ECG will be analysed and compared.
 
Patients can be recruited from different cardiology clinics; at the end of an exercise test to record sinus tachycardia, and in the catheter lab during electrophysiological studies/ ablation procedures to record arrhythmias.
 
Every patient will be counselled about the project by a member of the cardiology / research team (doctor or qualified research nurse) and will be provided with a patient information sheet. Patients will be given up to 2 weeks to consider participation in the study. If in agreement, written informed consent will be obtained.
 
A 30-second ECG tracing will be obtained by simply holding the Smartphone and placing at least 1 finger from each hand on electrodes embedded into the back of the Smartphone case (figure 2). For sedated patients in the catheter lab, AliveCor electrodes will be placed and taped on patient chest wall, left parasternal third intercostal space. The AliveCor ECG tracing will be recorded as close to simultaneously as the 12 lead ECG

	recording as possible.
Duration	2 years
Participating Centres	Blackpool Victoria Hospital
Primary End Point	Screening characteristics and diagnostic accuracy of AliveCor ECG recordings to detect cardiac arrhythmias
Number of participants	400
Main Inclusion /Exclusion Criteria	
Inclusion:
 
 • Male or female patients >18 years with 12 lead ECG finding of arrhythmia, manifest pre-excitation, pacing rhythm, sinus rhythm or sinus tachycardia. 
Exclusion Criteria:
 
 • Patients <18 years of age. • Patients unable to or unwilling to use the device.

Statistical Methodology and Analysis	
400 patients are planned to be recruited as follows:
 
50 patients with supraventricular tachycardia (SVT) 50 patients with atrial flutter (AFl) 50 patients with atrial fibrillation (AF) 50 patients with ventricular tachycardia (VT) 50 patients with manifest pre-excitation 50 patients with sinus tachycardia to constitute the tachycardia control group
 
100 normal ECGs will also be collected from the first 100 patients who have regular sinus rhythm to constitute the sinus rhythm control group.
 
ECGs will be recorded in duplicate, with one recording being made using the AliveCor device, and one recording being made using a normal 12-lead ECG. Recordings will be undertaken as close to simultaneously as possible. The ECG diagnosis will be made by the lead Electrophysiologist on the 12-lead ECG so produced and this will be taken as the correct ECG diagnosis.
 
All ECGs (both 12-lead and AliveCor) will be reported by a Consultant Electrophysiologist, a General Cardiologist and a General Practitioner, blinded to the full study protocol and the patient allocation group. The output of the AliveCor algorithm for automatic ECG diagnosis will also be recorded. The readers will firstly read the AliveCor ECGs and at a later date read the 12-lead ECGs to prevent comparisons between the ECGs and to give accurate screening characteristics for AliveCor ECGs.
 
The diagnostic accuracy and screening characteristics of ECGs generated by the AliveCor device will be reported for each arrhythmia individually and in combination both by each reporter. To calculate screening characteristics, ECGs of sinus rhythm and sinus tachycardia will also be included in each analysis as normal controls. 95% confidence intervals will be calculated.
 
The primary end-point will be the sensitivity and screening characteristics of detecting each arrhythmia individually and in combination by each reporter using the AliveCor device, calculating 95% confidence intervals.
 
The binomial exact calculation would be used to calculate confidence intervals.
 
With a sample size of 50 patients with one arrhythmia, a sensitivity of 80% would produce a 95% confidence interval of 68.9% to 91.1%. With a sample size of 250 (all arrhythmias combined), a sensitivity of 70% would produce a 95% confidence interval of 64.5% to 75.1%, i.e. an absolute error of $\pm 5\%$.
 
The main secondary end-point will be to compare the sensitivity of a

--------------------------------------	---------------------------------------------------------------------------------------------------------------------------------------------------------------------------------------------------------------------------------------------------------------------------------------------------------------------------------------------------------------------------------------------------------------------------------------------------------------------------------------------------------------------------------------------------------------------------------------------------------------------------------------------------------------------------------------------------------------------------------------------------------------------------------------------------------------------------------------------------------------------------------------------------------------------------------------------------------------------------------------------------------------------------------------------------------------------------------------------------------------------------------------------------------------------------------------------------------------------------------------------------------------------------------------------------------------------------------------------------------------------------------------------------------------------------------------------------------------------------------------------------------------------------------------------------------------------------------------------------------------------------------------------------------------------------------------------------------------------------------------------------------------------------------------------------------------------------------------------------------------------------------------------------------------------------------------------------------------------------------------------------------------------------------------------------------------------------------------------------------------------------------------------------------------------------------------------------------------------------------------------------------------------------------------------------------------------------------------------------------------------------------------------------------------------------------------------------------------------------------------------------------------------------------------------------------------------------------------------------------------

	
Consultant Electrophysiologist in detecting all arrhythmias using the AliveCor device vs the originally coded 12-lead ECG, to test whether the AliveCor device is non-inferior to the original 12-lead ECG diagnosis. Assuming a 95% one-sided confidence interval and a power of 80%, if there is a true difference in sensitivity in favour of the 12-lead ECG over an AliveCor ECG of 10%, and then a sample size of 301 would be needed to exclude a difference in favour of the 12-lead ECG of more than 16%.
 
Further secondary end-points will be to compare a Consultant Electrophysiologist with a General Consultant Cardiologist with a General Practitioner and with the automated AliveCor ECG diagnosis using their automatic algorithm.

--	----------------------------------------------------------------------------------------------------------------------------------------------------------------------------------------------------------------------------------------------------------------------------------------------------------------------------------------------------------------------------------------------------------------------------------------------------------------------------------------------------------------------------------------------------------------------------------------------------------------------------------------------------------------------------------------------------------------------------------------------------------------------------

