After the AliveCor Heart Monitor has taken a reading, it is sent wirelessly by a patented high frequency sound transmission to the mobile device, where it can be viewed using the AliveECG (Kardia) app. If or when the device has a suitable Wi-Fi or mobile connection, the recording will automatically synchronise with the secure encrypted AliveCor cloud server. The user can also send the recording directly to a relevant healthcare professional, such as a GP, to be read using the Provider Dashboard, which is a web-based application run from any standard PC.^{4,5} For this study, we will only use trust enabled devices such as iPod/iPad available in Cardiology department- Cardiac Investigation Unit (CIU).

Cost:

The AliveCor system consists of an AliveCor Heart Monitor and the Kardia app. The AliveCor Heart Monitor costs £62.49, excluding VAT, for a single unit. For orders of 50 units or more, the price reduces to £50 each, excluding VAT. The Kardia app is available as a free download from the Apple App Store or from Google Play, and the web-based Provider Dashboard is free to use. The estimated cost of a standard 12-lead ECG, in which a practice nurse applies the test and a GP reviews the results, to be £36.33 with the cost of an ambulatory ECG as £170 (NICE 2014).²

Evidence from literature

- To date, the device has been used in current practice to improve the detection of recurrent AF⁶ and to reliably monitor the QTc interval.⁷
- Lowres et al. (2014)⁵ conducted a community-based, opportunistic screening programme of 1000 people aged 65 years and over, using the AliveCor Heart Monitor to detect AF. The study was set in 10 pharmacies in Sydney, Australia. Following the analysis of 996 readings, excluding 4 people with pacemakers, the AliveECG app had 98.5% sensitivity (67/68; 95% CI 92.1%–100%) and 91.4% specificity (849/929; 95% CI 89.4–93.1%), using the cardiologists' diagnosis from the AliveCor Heart Monitor reading as the reference case.

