2.2 Study Objectives

Primary objectives: To assess the sensitivity and screening characteristics of AliveCor recording to detect a wide range of cardiac arrhythmias (AF, atrial flutter, SVT, VT, paced rhythm and pre-excitation) by 4 different readers.

Secondary Objectives:

- To test whether the AliveCor device will be non-inferior to the 12 lead ECG with respect to diagnosis of the arrhythmia when read by a Consultant Electrophysiologist.
- To compare the screening characteristics of the AliveCor's automated diagnostic algorithm with its screening characteristics when read by a Consultant Electrophysiologist, a general Consultant Cardiologist and a General Practitioner.

3 Study Design

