3.2 Primary Study Endpoints

Sensitivity and screening characteristics of AliveCor recording to detect cardiac arrhythmias.

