4.1.1 Inclusion Criteria

1	Male or female patients
2	Age > 18
3	12 lead ECG finding of sinus rhythm, arrhythmia and manifest pre-excitation

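### The sinus-rhythm controls are limited to normal, regular ECGs although eligibility asks only for sinus rhythm, which is likely to raise the specificity reported for AF, pre-excitation and all arrhythmias combined

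*Combined protocol and SAP*

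**What the plan says.** The selection rule for the sinus-rhythm controls appears once, in the Study Summary (section 1, Statistical Methodology and Analysis): "100 normal ECGs will also be collected from the first 100 patients who have regular sinus rhythm to constitute the sinus rhythm control group". The other control group is defined just before it: "50 patients with sinus tachycardia to constitute the tachycardia control group". That group carries no requirement that the ECG be normal or the rhythm regular.

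The same row says how the controls are used: "To calculate screening characteristics, ECGs of sinus rhythm and sinus tachycardia will also be included in each analysis as normal controls".

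Elsewhere the description is wider. The Methodology / Design row gives "150 control ECGs (100 sinus rhythm, 50 sinus tachycardia" and nothing more. Inclusion criterion 3 in section 4.1.1 reads "12 lead ECG finding of sinus rhythm, arrhythmia and manifest pre-excitation". The exclusions in section 4.1.2 cover age, inability or unwillingness to use the device, and implanted devices. Section 6 does not mention the controls.

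The primary endpoint in section 3.2 is "Sensitivity and screening characteristics of AliveCor recording to detect cardiac arrhythmias".

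**The concern.** Specificity depends on which non-diseased patients are tested. AF is recognised largely by irregularity, so a control group chosen for regular rhythm leaves out sinus-rhythm patients with ectopic beats or marked sinus arrhythmia, who are the obvious source of false AF calls. If *normal* also means a normal QRS and PR pattern, patients with bundle branch block or similar abnormalities are left out too. They are a natural source of false pre-excitation calls on a single-lead strip.

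The affected figures are part of the primary endpoint: specificity, and accuracy to the extent that it draws on the controls, for each of the three readers and the algorithm. Nothing in the documents says that the reported specificity would apply only to normal-ECG controls, so a reader of the results would take it as specificity in people with sinus rhythm. Patients never enrolled cannot be recovered in the analysis. The choice therefore has to be settled before the control group is filled.

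**Working it through.** **1. The plan's own count.** Cases: 5 × 50 = 250. Controls: 100 + 50 = 150. Total: 250 + 150 = 400, as stated. The sinus-rhythm group is 100/150, or two thirds, of the specificity denominator. The plan gives no expected specificity, target or precision for it, so there is no stated specificity to reproduce.

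**2. The texts side by side.**
- Study Summary, statistical row: normal ECGs, regular sinus rhythm.
- Study Summary, design row: sinus rhythm.
- Section 4.1.1: sinus rhythm.
- Section 4.1.2: no exclusion for ectopy, sinus arrhythmia or bundle branch block.

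The narrowing rests on two adjectives in one sentence, and no reason is given for it.

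**3. Illustrative size.** Every input in this step is an assumption, because the documents supply none of them:
- specificity in regular normal sinus-rhythm ECGs, s₀ = 97%;
- share of sinus-rhythm patients with a confusable ECG, f = 10% to 20%;
- specificity in those patients, s₁ = 80% to 50%;
- specificity in sinus tachycardia, 97%.

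Specificity in unselected sinus-rhythm patients = (1 − f) × s₀ + f × s₁:
- mild case: 0.9 × 0.97 + 0.1 × 0.80 = 0.953;
- severe case: 0.8 × 0.97 + 0.2 × 0.50 = 0.876.

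Specificity over all controls = (100 × sinus-rhythm value + 50 × 0.97) / 150:
- mild case: (95.3 + 48.5) / 150 = 95.9%;
- severe case: (87.6 + 48.5) / 150 = 90.7%.

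Under the current rule the figure is 97%. The gap is 97 − 95.87 = 1.1 points to 97 − 90.73 = 6.3 points.

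**4. Sensitivity to the assumptions.** The gap over the 150 is (2/3) × f × (s₀ − s₁), and the sinus-tachycardia value cancels out. With s₀ = 97%:
- f = 5%, s₁ = 90%: (2/3) × 0.05 × 0.07 = 0.2 points;
- f = 20%, s₁ = 80%: (2/3) × 0.20 × 0.17 = 2.3 points;
- f = 30%, s₁ = 60%: (2/3) × 0.30 × 0.37 = 7.4 points.

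**5. Against sampling error.** For 145/150 (96.7%) the exact 95% interval is 92.4% to 98.9%. A shift of a few points is similar in size to the interval's lower arm (96.7 − 92.4 = 4.3 points). The planned interval reflects only sampling from the selected controls and would not reveal the shift.

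**The case against.** The strongest reply is that *normal* is used loosely. The same row applies it to all 150 controls, sinus tachycardia included, and also to the standard 12-lead recording. It may mean only non-arrhythmic, in which case patients with bundle branch block are not excluded. This stands as a doubt, and it is why their exclusion is called probable. It does not explain *regular*, which on its face removes irregular sinus rhythm. If any sinus rhythm was intended, the sentence still conflicts with section 4.1.1 and could mislead a recruiter.

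It is also fair to say that the precision statements and the non-inferiority test concern sensitivity, which the choice of controls does not affect.

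A reader might infer more than the documents support:
- **That inflation is shown.** Only its likely direction follows from the text.
- **That the gap is 1.7 to 9.4 points**, by comparing 95.3% and 87.6% with 97%. Those values apply to the 100 sinus-rhythm controls alone, whereas the plan puts both control groups in each analysis.
- **That VT specificity is affected in the same way.** Sinus rhythm with a wide QRS at an ordinary rate lacks the tachycardia. The closer mimic is wide-QRS sinus tachycardia, and that control group carries no such restriction.
- **That the "91.4% specificity (849/929; 95% CI 89.4–93.1%)" in section 2.1 is a benchmark.** It is the app's AF result in a community pharmacy population, judged against cardiologists reading the same AliveCor trace.
- **That cases are easy to read** because section 4.2 recruits known positive findings. Known does not mean easy.
- **That the study claims primary-care specificity.** Section 2.1 names primary care as a possible use. Consecutive cardiology-clinic patients would not represent it either.

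**Conclusion.** The point holds as an avoidable restriction of the control spectrum, combined with an inconsistency between the Study Summary's statistical row and the eligibility text. Followed as written, it is likely to raise reported specificity for AF, pre-excitation and all arrhythmias combined, compared with what sinus-rhythm patients in general would give.

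The size is not known. The 1.1 to 6.3 points depend entirely on the assumed share of confusable ECGs and the assumed specificity in them; the wider set of assumptions gives 0.2 to 7.4. The calculation also uses one specificity for all confusable ECGs. In the per-arrhythmia analyses the effect will differ, since bundle branch block has no evident reason to produce AF calls. The change is worth making because it is cheap and cannot be made after recruitment, not because a large bias has been shown.

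**What to change.** Reconcile the Study Summary's statistical row with its design row and section 4.1.1, and carry the definition into section 6. Suggested wording: *The sinus-rhythm control group is the first 100 consecutive eligible patients whose 12-lead ECG shows sinus rhythm without manifest pre-excitation, with or without ectopic beats, sinus arrhythmia or bundle branch block.* The pre-excitation clause is needed because such patients are usually in sinus rhythm and form a case group.

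In addition:
- Record ectopy, sinus arrhythmia and QRS/PR abnormality on the CRF when the 12-lead is coded.
- State in section 6.2 that a reader who reports sinus rhythm with ectopy in such a control is scored as a true negative for the five target arrhythmias.
- Report specificity overall, for the regular normal subset, and separately for the sinus-rhythm and sinus-tachycardia controls.

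If the sponsor prefers to keep only regular normal ECGs, say so consistently and label the result as specificity against normal-ECG controls.

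The cost is a revised definition, a CRF entry, a scoring rule and some extra rows in a table. The number of controls, the clinics and the recordings do not change. Reported specificity will probably be somewhat lower, and the regular normal subset will be smaller than 100.

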3.1.1 General

Open label non-randomised diagnostic study. Readers will be blinded to the ECG diagnosis.

Expected study duration: 2 years

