3.1.2 Study procedure

Every patient will be counselled about the project by a member of the Cardiology / Cardiology research team (doctor or qualified research nurse) and will be provided with a patient information sheet. Patients will be given up to 2 weeks to consider participation in the study. If in agreement, written informed consent will be obtained.

A 30-second ECG tracing will be obtained by simply holding the Smartphone and placing at least 1 finger from each hand on electrodes embedded into the back of the Smartphone case (figure 2). For sedated patients in the cath lab, AliveCor electrodes will be placed and taped on patient chest wall, left parasternal third intercostal space. A 12-lead ECG will also be recorded as near to simultaneously as possible. The 12-lead ECG will be reviewed by Principal Investigator (PI) to ensure that the ECG rhythm has not changed.

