4.2 Participant Recruitment and Screening

Patients with known positive ECG findings can be recruited from different cardiology clinics, following exercise testing, and in the catheter lab during electrophysiological study/ ablation.

Every patient will be counselled about the project by a member of cardiology / research team (doctor or qualified research nurse) and will be provided by a patient information sheet. Patient will be given choice to take up to 2 weeks to consider participation in the study. If in agreement, written informed consent will be obtained.

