4.5 Withdrawal of Participants

Participants can withdraw from the study at any time. This study is a diagnostic study and does not involve follow up visit.

5 Study Procedures

- List of patients details (name and DOB) with study number will be kept safely in a locked cupboard in research office, cardiac education centre, Blackpool Victoria Hospital. This can only be accessed by Principal Investigator and research team members.
- Each patient will be given ID 'for example AC-001'. For 12 lead ECG 'AC-ECG-001' and for AliveCor recording 'AC-AliveCor-001'.
- A 30-second ECG tracing will be obtained by simply holding the Smartphone and placing at least 1 finger from each hand on electrodes embedded into the back of the Smartphone case (figure 2). For sedated patients in the catheter lab, AliveCor electrodes will be placed and taped on patient chest wall, left parasternal third intercostal space. The AliveCor ECG tracing will be recorded as close to simultaneously as the 12 lead ECG recording as possible.
- All 12 lead ECGs will be anonymised and kept safely in locked cupboard in research office, cardiac education centre, Blackpool Victoria Hospital. This can only be accessed by Principal Investigator and research team members.
- All data will be stored anonymously on the Trust Server in a folder called 'AliveCor Study'. This will be password protected. Only PI will have access to this folder.
- All AliveCor traces (anonymised) will be sent electronically via secure trust enabled device to the PI who will store these traces on folder 'AliveCor Study' as described above.

Figure 2

6 Statistical Plan

Statisticians within the Sponsor organisation wrote and designed the sample size calculation and statistical description method.

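### The reference diagnosis is not protected from sight of the AliveCor trace, and the non-inferiority test uses that same 12-lead diagnosis as its comparator

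*Combined protocol and SAP*

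**What the plan says.** **Reference.** Section 1 (Statistical Methodology and Analysis) says the diagnosis is "made by the lead Electrophysiologist on the 12-lead ECG so produced and this will be taken as the correct ECG diagnosis". No second reader or adjudication is described. Some arrhythmias are recorded in the catheter lab during electrophysiology studies or ablation (sections 1, 4.1, 4.2), but no section uses the findings of those studies in the reference.

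**Blinding.** Section 1 describes the three reporters as "blinded to the full study protocol and the patient allocation group". Section 3.1.1 says "Readers will be blinded to the ECG diagnosis". The separation in time is also theirs: "The readers will firstly read the AliveCor ECGs and at a later date read the 12-lead ECGs". None of these statements names the lead Electrophysiologist as reference coder.

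**Handling of traces.** Section 3.1.2: "The 12-lead ECG will be reviewed by Principal Investigator (PI) to ensure that the ECG rhythm has not changed". Section 5: "All AliveCor traces (anonymised) will be sent electronically via secure trust enabled device to the PI who will store these traces". Section 5 also gives the PI sole access to the study data folder. The documents do not say whether the PI, the lead Electrophysiologist and the Consultant Electrophysiologist who acts as reporter are the same person.

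**Comparator.** In sections 1 and 6.1 the main secondary endpoint compares the Consultant Electrophysiologist's AliveCor sensitivity with the 12-lead diagnosis as first coded. Section 6.2 describes the comparator differently, as a 12-lead ECG recorded at nearly the same time, and does not say whose reading of it counts.

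**The concern.** Two separate weaknesses sit in the reference standard.

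First, the plan separates AliveCor and 12-lead reads for the reporters so that one does not colour the other. It gives no such protection to the person whose call defines the truth in every primary analysis. If that person saw the AliveCor strip while settling a doubtful 12-lead, the reference could drift toward the index test and raise AliveCor's apparent sensitivity. Coding done that way cannot be undone later.

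Second, the 12-lead diagnosis is both the yardstick and one of the two things being measured. A 12-lead error then scores as correct for the 12-lead, and an AliveCor read that is right on that patient scores as wrong. This favours the 12-lead in the non-inferiority test.

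The two effects run in opposite directions. The exact confidence intervals planned in section 6.2 measure sampling error only and cover neither.

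**Working it through.** **1. Reproduce the plan's 301.** Inputs from section 6.1: one-sided 95% confidence interval, power 80%, true difference 10 points, margin 16 points. The two sensitivities are not given; 95% and 85% are back-solved assumptions. Unpaired formula with unpooled variance:

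n = (1.645 + 0.842)² × [p₁(1 − p₁) + p₂(1 − p₂)] / (0.16 − 0.10)²

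- 95% and 85%: 6.183 × (0.0475 + 0.1275) / 0.0036 = 300.5, so **301**, as stated.
- Other 12-lead sensitivities, same 10-point gap: 98% gives 216, 90% gives 430.
- A paired formula reaches 301 only with about 18.5% discordant pairs.

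**2. Put in what the plan's comparator implies.** If the coded 12-lead diagnosis is both reference and comparator, p₁ = 100% and p₂ = 90%:

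- 6.183 × (0 + 0.09) / 0.0036 = 154.6, so **155**. The paired formula agrees: discordance is then exactly 10%, and 6.183 × (0.10 − 0.01) / 0.0036 is the same figure.
- The test reduces to AliveCor sensitivity against a fixed 84%.
- Power with the 250 planned arrhythmias is 73% under 95%/85%. Under a fixed 100% it is 94% (normal approximation) or 88% (exact, needing at least 220/250 correct).

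On this reconstruction, the sample-size statement treats the 12-lead as fallible, while the endpoint wording makes it infallible.

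**3. Effect of one reference call recoded toward AliveCor.**

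- Ceiling, when a miss becomes a hit and the denominator stays fixed: 1/50 = 2.0 points in one group, 1/250 = 0.4 points combined.
- When the patient changes group, starting from 40/50 (80%) in each: a missed VT recoded as SVT gives VT 40/49 = 81.6% (+1.6) and SVT 41/51 = 80.4% (+0.4).
- In the combined figure, recoding between two arrhythmias adds nothing if any arrhythmia call counts as detection.

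**4. Effect of a wrong 12-lead reference.** If k of 50 patients coded to one arrhythmia have a different electrophysiology-study diagnosis (k is assumed), an AliveCor reader who is always right scores (50 − k)/50: 98% for k = 1, 90% for k = 5.

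**5. Illustration of direction (all values assumed).** True AliveCor sensitivity (Se) 80%, specificity (Sp) 95%, share with arrhythmia P = 250/400 = 0.625, reference error e from 2% to 10%.

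- Independent errors: [P(1 − e)Se + (1 − P)e(1 − Sp)] / [P(1 − e) + (1 − P)e]. At 2%, 0.4904/0.62 = 79.1%; at 10%, 0.4519/0.60 = 75.3%.
- Errors maximally shared with AliveCor's: at 2%, 0.5075/0.62 = 81.9%; at 10%, 0.5188/0.60 = 86.5%.
- A share r of misses recoded out of the arrhythmia group: 0.80/(1 − 0.20r). At r = 10% this is 81.6%; at r = 50%, 88.9%.

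The sign depends on the mechanism, and the documents give no reference error rate with which to choose among these.

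**The case against.** The strongest reply is that the 12-lead reference is a deliberate choice. The objective is AliveCor against a 12-lead ECG, and section 1 calls the 12-lead definitive. Electrophysiology findings exist only for catheter-lab patients, whose number is not given, so using them throughout would mix reference standards. That stands, and it is why they belong in a subset sensitivity analysis only. It does not answer the circular comparator.

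A reader might infer more than the text supports in four ways:

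- **That the reference depends on AliveCor.** Section 1 says the diagnosis is made on the 12-lead, and no section has the coder consult the strip. Protection is absent; contamination is not shown.
- **That the coder holds both traces.** This requires the PI to be the lead Electrophysiologist, which is not stated. Nor does section 5 say whether traces reach the PI before coding.
- **That the coder should be blind to recruitment group.** Section 4.2 says "Patients with known positive ECG findings can be recruited from different cardiology clinics" and the groups are themselves defined by the 12-lead finding, so the complaint is largely circular.
- **That any bias would be invisible.** Section 1 already has three blinded reporters read every 12-lead. Their disagreement with the reference would flag doubtful calls.

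The recoding mechanism is also weaker than it first looks. Results are reported by reporter, so a swayed coder creates a hit only for a reporter or algorithm that made the same call independently.

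**Conclusion.** The point holds in two parts of unequal strength. That the 12-lead diagnosis is both reference and comparator follows directly from sections 1 and 6.1: its sensitivity is 100% by construction and the comparison favours the 12-lead. The contrast between 301 and 155 supports this, but it rests on the assumed 95% and 85%. That the reference is unprotected from the AliveCor trace is an omission in the text, not evidence of a biased reference.

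The size of either bias is unknown. Per recoded call, 2 points in 50 and 0.4 points in 250 are ceilings. The illustrations show only that the distortion could go either way. This is an inexpensive improvement to conduct and analysis; it does not show that the planned results would be wrong.

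**What to change.** 1. **Lock the reference.** In section 1 (Statistical Methodology and Analysis) and section 5, state that the lead Electrophysiologist codes and locks the reference from the 12-lead alone before opening any AliveCor trace. Say whether this person is the PI or the Consultant Electrophysiologist reporter. Amend the trace routing and folder access in section 5 to match.
2. **Subset sensitivity analysis.** For patients recorded during an electrophysiology study, enter the study's final rhythm diagnosis on the CRF. In that subset, repeat the sensitivity and non-inferiority analyses with it as the reference for both the AliveCor reads and the blinded 12-lead reads already planned. Leave the main reference unchanged.
3. **Comparator.** In sections 1 and 6.1, define the 12-lead comparator as the Consultant Electrophysiologist's blinded 12-lead read, not the reference code, and align section 6.2. State that the main analysis still favours the 12-lead, because the reference comes from the same trace.

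Cost: protocol wording, a small access-rule change, one CRF field, one extra analysis and a short delay before traces are opened. The figures may prove less favourable. No added patients, recordings or readers are needed.
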